3.4 Determining PAD diagnosis from Index test results

For each index test, a participant is defined as having a positive result in PAD if they have recorded the following criteria ***in either vessel (i.e. Dorsalis pedis OR Posterior tibial):***

1. Audible waveform assessment: monophasic waveform.
- 2a. Visual waveform assessment: monophasic ***OR*** biphasic waveforms with adverse features.
- 2b. Podiatry ankle duplex (PAD) scan: monophasic or biphasic waveforms with adverse features.
3. ABPI: ABPI (DP) ≤ 0.9 ***OR*** ABPI (PT) ≤ 0.9 in the limb being assessed.
4. TBPI: TBPI < 0.75 in the limb being assessed.
5. Exercise ABPI: Exercise ABPI (DP) ≤ 0.9 ***OR*** Exercise ABPI (PT) ≤ 0.9 in the limb being assessed.

For tests that have measurements for the right and left limbs, we are only interested in the limb that was assessed, i.e. in response to the question in section ‘Index Tests (Repeat 1) ‘Which limb is being assessed?’.

Each criteria assessment above, except TBPI, has two vessels, a ‘Dorsal pedis artery (DP)’ and ‘Posterior tibial artery (PT)’. If both vessels are completed then a PAD diagnosis is determined as follows:

- DP(+ve) + PT(+ve) = PAD(+ve)
- DP(+ve) + PT(-ve) = PAD(+ve)
- DP(-ve) + PT(+ve) = PAD(+ve)
- DP(-ve) + PT(-ve) = PAD(-ve)

There may be a case where either the DP or PT vessel has been recorded, not both. When this is the case a comment as to why this vessel is missing should be recorded:

- DP(+ve) + PT(missing) = PAD(+ve)
- DP(missing) + PT(+ve) = PAD(+ve)
- DP(-ve) + PT(missing) = PAD(inconclusive)
- DP(missing) + PT(-ve) = PAD(inconclusive)

When a diagnosis of PAD is inconclusive, these cases will be recorded and reported but shall not be used in the final analysis.

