3.5 Determining PAD diagnosis from Reference test results

In the CRF ‘DM-PAD_CRFs_CTA MRA Core Lab Reporting_Version 1.0_02082021’, there is a section on Right and Left Leg ANGIO scores. These scores are to be used to determine whether a participant has a diagnosis of PAD or not. One score should be selected for each artery.

The database captures if the participant has overall PAD however, for the analysis we need to determine if a participant has PAD in the left or right leg, which ever limb was being assessed (defined from the ‘Repeat Index Tests’ CRF: ‘Which limb is being assessed?’).

For each participant, for each leg, the total of all the scores shall be calculated which determines the following diagnoses:

- No PAD: Total score of 0
- PAD: Total score ≥ 1

Only the result on the limb being assessed is to be used in the analysis.

4. Final Analysis

This analysis plan describes the end of trial statistical analyses to be performed on DM PAD by the ECTU statistics team.

There are no statements in the report declaring what the optimal cut-point is from the ROC analysis. The optimal cut-point is that with the highest sensitivity and highest specificity, if the “cost” of incorrectly identifying a participant without PAD is the same as the “cost” of incorrectly identifying a participant with PAD. However the cut-point with the highest sensitivity cut-point is often not the same as the cut-point with the highest specificity so the final decision on the optimal cut-point needs to be a clinical decision.

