4.6 Sensitivity analysis

Missing data

A sensitivity analysis may be performed in which missing primary outcome data are imputed. The robustness of the findings to any observed patterns of missing data will be assessed, which are expected to differ by test. The imputation method will be determined at time of analysis, taking into consideration the choice of assumptions such as missing at random (MAR) or missing not at random (MNAR) depending on reasons for loss to follow-up[3].

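### A limb with one vessel recorded counts in the primary sensitivity only if that vessel is positive, and nothing in the SAP commits to imputing or bounding the excluded results

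*SAP*

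**What the plan says.** SAP 3.4 calls a test positive if either the dorsalis pedis (DP) or the posterior tibial (PT) vessel meets its criterion. TBPI has a single reading, so the two-vessel rule covers the other four primary tests and the exploratory PAD-scan.

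When one vessel is unrecorded, a positive in the other settles the result ("DP(+ve) + PT(missing) = PAD(+ve"), but a negative does not ("DP(-ve) + PT(missing) = PAD(inconclusive"). The same holds with the vessels exchanged. For the unsettled results the SAP states: "When a diagnosis of PAD is inconclusive, these cases will be recorded and reported but shall not be used in the final analysis". It also asks that "a comment as to why this vessel is missing should be recorded".

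The text on missing data is general:
- Protocol 8.4, copied into SAP section 2, commits to multiple imputation under missing at random, with missing-not-at-random analyses in addition. It describes the latter as probably closer to the likely mechanism.
- SAP 3.3 makes complete-case analysis the default.
- SAP 4.6 says "The robustness of the findings to any observed patterns of missing data will be assessed, which are expected to differ by test", but also "A sensitivity analysis may be performed in which missing primary outcome data are imputed". The method is left until the analysis, with a choice between "missing at random (MAR) or missing not at random (MNAR) depending on reasons for loss to follow-up".

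**The concern.** Calling a lone positive positive is right under the either-vessel definition. The difficulty is the treatment of its counterpart. Among one-vessel limbs, positives stay in numerator and denominator, and negatives leave both. Some of those negatives would have been positive on the second vessel and some not. Removing all of them conditions the analysis set on the test result.

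Sensitivity is the primary endpoint. The planned counts and flow chart would show how many results were dropped, but not how far the estimate could move. That needs the inconclusives split by reference status, which SAP 3.4 does not promise.

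The general missing-data text does not clearly close the gap. Loss to follow-up is not why a vessel goes unrecorded at visit 1. SAP 4.6 also sits under the heading "4. Final Analysis", so on a literal reading SAP 3.4 keeps inconclusive results out of the sensitivity analysis too.

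**Working it through.** **Inputs from the documents.** There are 255 limbs with PAD and 255 without (Protocol 8.1). An exact one-sided binomial calculation at 1% with 90% power, sensitivity 90% and a margin of 8.2 points reproduces 255 per group. TrEAD sensitivities are taken as true values: ABPI 60%, audible Doppler 74%, visual Doppler 83%, PAD-scan 95% (Protocol section 1).

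**Assumptions.** The share *m* of limbs with exactly one vessel recorded is not given; 2, 5, 10 and 20% are tried. Single-vessel positivity *s* comes from a bivariate normal with equal thresholds and correlation 0.6. It is 45.3% when two-vessel sensitivity *S* is 60%, 59.7% at 74%, 66.6% at 80%, 70.3% at 83% and 88.0% at 95%.

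**1. Missingness unrelated to either vessel's result, within reference status.**

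Reported sensitivity = [(1−m)S + ms] / [(1−m) + ms], so bias = ms(1−S) / [1 − m(1−s)].

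For S = 0.60 and m = 0.10: (0.540 + 0.0453) / (0.900 + 0.0453) = 0.619.

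Overstatement in points:

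| True sensitivity | m=2% | 5% | 10% | 20% | 99% half-width, n=255 |
|---|---|---|---|---|---|
| 60% | 0.4 | 0.9 | 1.9 | 4.1 | 7.9 |
| 74% | 0.3 | 0.8 | 1.6 | 3.4 | 7.1 |
| 83% | 0.2 | 0.6 | 1.2 | 2.5 | 6.1 |

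At 95% the bias is at most 0.9 points. At true 60%, moving the correlation from 0 to 0.9 changes the m = 10% figure only between 1.6 and 2.2.

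Specificity takes the same form with the false-positive rate in place of S. For a rate of 10%, s = 6.0% and m = 10%: 0.096/0.906 = 10.6%, so a specificity of 90% is understated by 0.6 points (0.1 to 1.3 over the range of m).

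**2. Share needed for a 2-point shift.** Solving the bias formula, m = 0.02 / [s(1−S) + 0.02(1−s)]. This gives 10.4% at true 60%, 12.2% at 74% and 15.9% at 83%.

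**3. Coverage of a 99% interval at true 60%.** Exact binomial with Wilson limits on the expected number included (252, 248, 241, 227) gives 99.0, 98.7, 97.9 and 91.9% at m = 2, 5, 10 and 20%.

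**4. Other mechanisms.**
- If the second vessel is skipped only after a positive first vessel, no negative is lost and the bias is zero.
- Suppose an abnormal vessel is k times as likely to be unrecorded, with m held at 10%:

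| k | 1 | 2 | 3 | 4 | 5 | 10 |
|---|---|---|---|---|---|---|
| Bias, true 60% | +1.9 | +0.8 | +0.3 | −0.1 | −0.3 | −0.9 |
| Bias, true 80% | +1.4 | +0.6 | +0.3 | +0.1 | 0.0 | −0.2 |

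**5. Bounds.** Under the mechanism in step 1, counting all inconclusives negative gives (1−m)S + ms, and counting all positive gives (1−m)S + m. For 255 PAD limbs at true 60%:

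| m | Expected inconclusive | Bounds |
|---|---|---|
| 2% | 2.8 | 59.7–60.8% |
| 5% | 7.0 | 59.3–62.0% |
| 10% | 13.9 | 58.5–64.0% |
| 20% | 27.9 | 57.1–68.0% |

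For specificity of 90% at m = 10%, about 24 of 255 limbs are dropped and the bounds are 81.0–90.4%. In the informative scenario at true 60% and k = 10, the rule gives 59.1% and the bounds are 56.8–60.7%. The two-vessel value among limbs with at least one vessel recorded is 59.9%, inside the bounds. The bounds held that value at every k tried, for true 60% and 80%.

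**The case against.** The one-vessel share is unknown, and SAP 3.4 presents the situation only as a possibility. At 5% or less the bias is about 1 point, small beside half-widths of 6 to 8 points. The 20% column looks extreme. With sensitivity 60% and specificity 90%, about 28 + 48 = 76 of 510 results (15%) would be inconclusive on one test, against reported attrition of 13%. The documents do not say whether that 13% includes inconclusives. The protocol itself favours missing not at random, and for k between 3 and 5 the bias nearly vanishes. The general imputation commitment can be read to reach an unrecorded vessel, the reason for the gap is collected, and the SAP's 2×2 table is already laid out by reference status. Finally, the final analysis named in SAP 3.4 may mean only the main estimate.

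Most of this stands as a limit on size. A material bias of known direction is not shown, and the reading of the section heading is one of two. It does not remove the gap, because no text names inconclusive or one-vessel results for imputation or bounding. Uncertainty about mechanism is itself a reason to prespecify bounds. An analysis restricted to limbs with both vessels recorded would be unbiased under step 1. It would be biased if the second vessel is skipped after a positive first, so it does not replace the bounds.

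**Conclusion.** The concern holds and should be fixed. For four of the five primary tests the SAP makes inclusion depend on the result and does not commit to showing the effect. Confidence is high for the rule and the gap, and not for the size. Under unrelated missingness and vessel correlation 0.6, sensitivity is overstated by about 1 point or less when up to 5% of limbs have one vessel recorded. At 20% the overstatement reaches 4.1 points for a test with true sensitivity 60%. Informative missingness can cancel or reverse this. No net direction is claimed for comparisons with TBPI, which has its own exclusion: Protocol 8.1 reports that it could not be performed in 20% of TrEAD patients.

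**What to change.** 1. **SAP 3.4 and 4.4.** Tabulate inconclusive results by test and reference status. Beside the primary estimate for each two-vessel test, give sensitivity and specificity with every inconclusive counted negative and with every one counted positive. Among limbs with at least one vessel recorded, this range contains the two-vessel value whatever the mechanism.
2. **SAP 3.4.** Limit the exclusion to the primary estimate, so that SAP 4.6 can use these cases. Possible wording: *Inconclusive results are left out of the primary estimate. They will be tabulated by test and reference status, and sensitivity and specificity will be shown with all of them taken as negative and with all of them taken as positive.*
3. **SAP 4.6.** Restore the protocol's firm commitment to multiple imputation with missing-not-at-random variants, and state that it covers an unrecorded vessel.

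The cost is a few extra table rows per two-vessel test and modest programming. No new data are needed: vessel-level results and the reason for a missing vessel are already to be recorded. The primary estimate is unchanged.

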3.5 Determining PAD diagnosis from Reference test results

In the CRF ‘DM-PAD_CRFs_CTA MRA Core Lab Reporting_Version 1.0_02082021’, there is a section on Right and Left Leg ANGIO scores. These scores are to be used to determine whether a participant has a diagnosis of PAD or not. One score should be selected for each artery.

The database captures if the participant has overall PAD however, for the analysis we need to determine if a participant has PAD in the left or right leg, which ever limb was being assessed (defined from the ‘Repeat Index Tests’ CRF: ‘Which limb is being assessed?’).

For each participant, for each leg, the total of all the scores shall be calculated which determines the following diagnoses:

- No PAD: Total score of 0
- PAD: Total score ≥ 1

Only the result on the limb being assessed is to be used in the analysis.

4. Final Analysis

This analysis plan describes the end of trial statistical analyses to be performed on DM PAD by the ECTU statistics team.

There are no statements in the report declaring what the optimal cut-point is from the ROC analysis. The optimal cut-point is that with the highest sensitivity and highest specificity, if the “cost” of incorrectly identifying a participant without PAD is the same as the “cost” of incorrectly identifying a participant with PAD. However the cut-point with the highest sensitivity cut-point is often not the same as the cut-point with the highest specificity so the final decision on the optimal cut-point needs to be a clinical decision.

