Scans will be assessed using a validated angiographic scoring system (ANGIO score) (33); 10 major arteries supplying the lower limbs are each scored according to the degree of stenosis (0, 0-49% stenosis; 1, non-occlusive stenosis of $\geq 50\%$; 2, complete occlusion). The presence of one or more arterial lesions of $\geq 50\%$ stenosis will be used as threshold for the diagnosis of PAD. Tandem lesions with a combined value of $\geq 50\%$ will also be considered positive for PAD as they are haemodynamically significant and in certain scenarios (e.g., non-healing DFU) may prompt treatment. PAD severity will also be categorised according to the ANGIO score, as mild (≤ 4), moderate (5-9) or severe (≥ 10). These categories have been shown to correlate with risk of amputation and cardiovascular events (33).

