- 2a. Visual handheld Doppler
- 2b. PAD-scan (in 4 selected centres)¹
3. Toe-brachial pressure index (TBPI)
4. Ankle-brachial pressure index (ABPI)
5. Exercise ABPI i.e. ABPI performed following repetitive heel raising.

Participants will firstly be assessed via remote screening. If considered eligible, they will be invited in for a face-to-face appointment (i.e. Visit 1) alongside a routine/planned visit. They will then be invited for a reference scan (i.e. Visit 2) within 6 weeks of Visit 1. Finally a subset of patients will be invited to a 1 year follow up. The target sample size is 584 participants from 18 sites.

This document has been compiled according to the Edinburgh Clinical Trials Unit (ECTU) standard operating procedure (SOP) "Statistical Analysis Plans" ECTU_ST_04 and has been written based on information contained in the study protocol version 5.0 25 July 2022.

2. Statistical Methods section from the protocol

The five individual tests (and the sixth exploratory test in four sites) will be compared against the reference test (CTA/MRA), calculating standard diagnostic accuracy metrics of sensitivity, specificity, predictive values, likelihood ratio, and diagnostic odds ratio (using the bivariate model approach implemented in R).

95% confidence intervals calculated at 99% to adjust for the five comparisons will be presented.

The robustness of the findings to any observed patterns of missing data will be assessed, which are expected to differ by test. A multiple imputation approach will be used assuming the data are missing at random. In addition, and probably more consistent with the likely missing data generating mechanisms, sensitivity type analyses assuming the data are missing not at random (i.e. informatively missing) will be explored. This would attempt to identify different types of missing data by an underlying reason or reasons, and then imputing values that capture plausible measurements for those missing data. The (gamma) γ -adjustment approach given by van Buuren will be followed (Flexible Imputation of Missing Data, Chapman and Hall, 2018, section 3.8ff), and also the recommendations of Molenburghs & Kenward (Missing Data in Clinical Studies, Wiley, 2007; Section 19ff on sensitivity analyses). These approaches would allow the set of reasons for missing values to vary across the tests. The purpose is to stress the calculated findings to test their robustness to the observed patterns of missing data.

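### SAP 3.5 derives reference-standard PAD from the limb's ANGIO total alone and has no term for the protocol's tandem-lesion rule

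*SAP*

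**What the plan says.** Protocol 5.8 describes the core-lab reading. Ten arteries are each scored by degree of stenosis: "0, 0-49% stenosis; 1, non-occlusive stenosis of" at least 50%, and 2 for complete occlusion. PAD is then defined by two routes. The first is one or more lesions of at least 50%. The second is additional: "Tandem lesions with a combined value of" at least 50% "will also be considered positive for PAD as they are haemodynamically significant and in certain scenarios". The section does not define the combined value and does not say what artery score a tandem pair receives.

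SAP 3.5 says of the ANGIO scores: "These scores are to be used to determine whether a participant has a diagnosis of PAD or not". It adds: "One score should be selected for each artery". The scores are totalled for each leg and only the assessed limb is used. The rule is "No PAD: Total score of 0", and PAD for a total of 1 or more. The database's own PAD field is set aside because it is held per participant: "The database captures if the participant has overall PAD however, for the analysis we need to determine if a participant has PAD" in the assessed leg. Tandem lesions are not mentioned anywhere in the SAP.

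**The concern.** The SAP rule carries over the protocol's first route to PAD and is silent on the second. Two or more lesions, each below 50%, can meet the protocol's tandem criterion while every artery, scored on its individual lesions, gets 0. The SAP total is then 0 and the limb enters the analysis as non-diseased.

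The variable at stake is the reference standard. SAP 4.4 makes sensitivity against it the primary outcome. Specificity, likelihood ratios, predictive values, the diagnostic odds ratio, the ROC analysis, the combination models and the subgroup tables split by PAD status all use it too. A misclassified tandem-only limb moves from the sensitivity denominator to the specificity denominator for every index test at once. A test that missed it gains a true negative in place of a false negative. A test that detected it is charged with a false positive.

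**Working it through.** The plan states no figure on this point, so there is none to reproduce. The check compares the two rules on example limbs and then converts one reclassified limb into percentage points.

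**1. The two rules on four limbs**

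| Assessed limb | Protocol 5.8 | SAP 3.5 |
|---|---|---|
| No lesion | No PAD | No PAD |
| Single lesion of at least 50% | PAD | PAD |
| Tandem only, an artery scored 1 | PAD | PAD |
| Tandem only, all arteries scored 0 | PAD | No PAD |

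The rules part only in the last row. Whether that row occurs depends on a scoring convention that neither document gives. Within one artery, the reader could enter the combined value as 1, and the SAP total would then be right. For lesions in two arteries, one score per artery has no evident place for a combined value unless a convention assigns it to one of them.

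**2. Could version lag explain the gap?** The SAP "has been written based on information contained in the study protocol version 5.0 25 July 2022", while the current protocol is version 7.0. The revision history lists the recruitment extension for version 6.0, and the sample size reduction and number of PAD-scan centres for version 7.0. None of these touches the reference definition.

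**3. Is it a declared departure?** SAP 4.5.2 states and justifies its change of method for test combinations. SAP 3.5 declares no change, and SAP 3.1 says all protocol analyses except the internal pilot are addressed.

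**4. What one limb is worth.** Inputs from Protocol 8.1: 255 limbs with PAD, 255 without, and sensitivity (Se) and specificity (Sp) of 0.80 or 0.90. Move one limb from PAD to No PAD.

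Index test negative in that limb:
- Se shift = 255·Se/254 − Se = Se/254: 0.80/254 = +0.315 points; 0.90/254 = +0.354 points.
- Sp shift = (255·Sp + 1)/256 − Sp = (1 − Sp)/256: 0.20/256 = +0.078 points; 0.10/256 = +0.039 points.

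Index test positive in that limb:
- Se shift = (255·Se − 1)/254 − Se = −(1 − Se)/254: −0.20/254 = −0.079 points; −0.10/254 = −0.039 points.
- Sp shift = 255·Sp/256 − Sp = −Sp/256: −0.80/256 = −0.313 points; −0.90/256 = −0.352 points.

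This is a conversion per limb. The documents give neither the frequency of tandem-only limbs nor the index-test positivity in them, so it cannot be scaled to an estimated bias.

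**The case against.** The strongest reply is that the SAP is silent rather than contradictory. Protocol 5.8 can be read as telling the radiologist what counts as a 50% result when the score is entered. SAP 3.5 works one step later, on recorded scores. On that reading a total of 1 or more already includes tandem disease. The core-lab reporting form that SAP 3.5 cites may say so. It is not part of the two documents, and a short stretch of the protocol before the imaging appendix was not available for this check. The protocol also never says that tandem lesions can span two scored arteries. Setting aside the overall PAD field is reasonable, since it is not specific to a limb.

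The possible effect may also be small against sampling error. With 255 PAD limbs a simple 99% half-width, 2.576·√(Se(1 − Se)/255), is 4.8 points at 90% and 6.5 points at 80%. Moving k index-negative limbs shifts sensitivity by Se·k/(255 − k). Matching those half-widths takes about 13 limbs (0.90 × 13/242 = 4.8 points) or 19 limbs (0.80 × 19/236 = 6.4 points). If index positivity in tandem-only limbs is close to the test's overall sensitivity, sensitivity hardly moves, although specificity would fall.

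Much of this stands. The benign reading is possible, misclassification is not shown, and the cross-artery case is an inference. But the printed score puts 0-49% at 0, the protocol presents the tandem rule as an addition to the single-lesion threshold, and neither document states the convention that would join the two. The second programming planned in SAP section 5 would not find the problem, because both programmers would follow the same rule.

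**Conclusion.** The point holds as a mismatch in the text. Applied as printed, the protocol's artery score and the SAP's total-score rule call a tandem-only limb non-diseased where the protocol calls it PAD, and the SAP declares no departure. Confidence in that is high.

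The numerical consequence is unknown. It is zero if tandem disease was scored as 1. Otherwise it depends on how many limbs are tandem-only and how each index test reads in them. It should be fixed before analysis because it concerns the reference variable for the primary outcome and costs little to settle.

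**What to change.** 1. Before database lock, ask the core lab to confirm in writing how tandem lesions were scored, within one artery and across arteries, and whether the overall PAD field includes them.
2. Amend SAP 3.5 to match Protocol 5.8:
   - If tandem lesions were scored 1, state that a total of 1 or more includes them. The derivation does not change.
   - If not, define PAD as a total of at least 1, or tandem lesions with combined stenosis of at least 50% in the assessed limb, taken from existing core-lab records. Where the overall PAD field carries the tandem rule, limit queries to assessed limbs with total 0 in participants whose overall field is positive. Protocol 5.8 has the core-lab radiologist blinded, and queries should stay under that blinding.
   - If no existing record holds tandem status, say in the SAP and the report that the score-only reference departs from Protocol 5.8.
3. If the two rules differ in any limb, report the score-only rule as a sensitivity analysis.

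The cost is one written question and one SAP sentence. If tandem lesions were not scored 1, add one derived variable and some data queries. No new scans, participants or general re-reading of limbs scored 0 are needed.
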